## **Design**

---

Prospective Biomedical Intervention or Experiment

## **Study Procedures**

---

### **Recruitment/Participant Identification Process:**

**In-PERSON CONTACT:** Participants will be recruited from the practices of the Principle Investigator and the Co-Investigators, the clinics of the University of Utah Orthopaedic Center, University of Utah Farmington Clinic, and the University of Utah South Jordan Health Center, and other University of Utah Hospital and Clinic locations. If the participant appears to be a candidate, he or she will be invited to participate.

**WRITTEN OR ELECTRONIC CHART REVIEW** will also be used to identify potential study participants on the PI and Co-PIs clinical and procedure schedules. The PI, Co-PIs, Clinical Research Coordinator, and Study Coordinator will perform the chart review to determine eligibility.

**REFERRALS:** Additional recruitment from University of Utah Hospitals and Clinics and local prosthetic offices. Flyers will be posted and information readily available for primary care providers to refer to the PM&R spine clinic. Flyers will be posted in waiting rooms, and clinic bulletin boards.

Participants will be personally invited to participate by either the PI or the Co-PI's either in person while in their respective clinics.

**Informed Consent:**

**Description of location(s) where consent will be obtained:**

Consent will be obtained at one of these University of Utah clinic locations: University of Utah Orthopaedic Center University of Utah South Jordan Health Center University of Utah Farmington Health Center

**Description of the consent process(es), including the timing of consent:**

As participants are identified by the PI or CO-I's as being possible candidates for this study they will invited to participate. It is anticipated that most subjects in this study will be identified mainly through the regular flow of the University of Utah clinics. The informed Consent process will occur either at the time the subject is in clinic or the participant may elect to complete the process at a later time. The patient will be greeted by the investigator or one of the study staff team members while in clinic. Patients will be given an IRB approved informed consent. All elements of the consent will be discussed with the participant, asking questions to assure they understand what is being asked of them. The patient will be allowed as much time as needed to consider fully if they would like to participate in the study. The patient will be encouraged to ask questions and if necessary take the consent home to discuss with family members and or other health care providers. The subject will be given sufficient time needed to review, ask and have his or her questions answered for a full understanding of the study and the procedures along with the risks and benefits. When the participant's questions have been fully answered, we will have the patient sign consent prior to their planned procedure. Participants will be informed that participation is voluntary and that they may withdraw from the study at any time, without prejudice. A copy of the informed consent document will be given to the participants for their records. The informed consent process will be conducted and documented in the source document (including the date), and the form signed, before the participant undergoes any study-specific procedures. The rights and welfare of the participants will be protected by emphasizing to them that the quality of their medical care will not be adversely affected if they decline to participate in this study.

## **Procedures:**

Screening Visit: As participants are identified by the PI or CO-I's as being possible candidates for this study they will be invited to participate. Main inclusion requirement, as listed in inclusion criteria, is that the patient is being scheduled for residual limb neuroma radiofrequency ablation (RFA) procedure as standard of care. If patient states interest in the study and wishes to discuss in more detail a research coordinator will discuss at time of appointment or call and answer any questions at a time convenient to the patient. If patient is interested, and does meet inclusion/exclusion criteria, and does not have time to do the baseline questions at time of appointment a qualified research staff member will call the patient to complete by phone. It is anticipated that most subjects in this study will be identified mainly through the regular flow of the University of Utah clinics. The informed Consent process will occur either at the time the subject is in clinic or the participant may elect to complete the process at a later time. Eligibility is determined by the inclusion and exclusion criteria. Qualifying volunteers will be asked to provide both written and verbal informed consent once a standard of care treatment plan has been agreed upon by the patient and treating physician.

Baseline: Participants who meet inclusion and exclusion criteria will be enrolled into the study after consenting to participate and before receiving residual limb neuroma RFA. This procedure is considered standard of care and are typically based on physician preference. Baseline data will be collected within 2 weeks prior to the scheduled procedure, this will include information from their examination and baseline questionnaires which include the following:

An electronic data collection system (REDCap via computer) will be used to record all pre-procedure and follow-up data as listed above (See attached PDF for baseline survey)

1. Age (years).
2. Sex
3. Height (cm).
4. Weight (Kg).
5. Duration of pain (weeks).
6. Date of amputation
7. Etiology of amputation
8. Level of amputation
9. Radiologic diagnosis based on ultrasound of residual limb.
10. Patient-Reported Outcomes Measurement Information System (PROMIS) 10
11. Analgesic medication log: dose and frequency of each medication
12. Brief Pain Inventory (BPI) with modification to include numerical rating scale (NRS) score (worst, least, average, current).
13. Groningen Activity Restriction Scale (GARS)
14. Pinprick Sensory Threshold (Von Frey Hair testing at the neuroma site)
15. Pressure Pain Threshold (algometer testing at the neuroma site)

Additional questions for post procedure survey

16. Patient Global Impression of Change (PGIC)

Patient satisfaction score (five-point Likert scale: 1, very dissatisfied; 2, dissatisfied; 3, neither satisfied nor dissatisfied; 4, satisfied; and 5, very satisfied)

Immediately after ablation the following will be obtained:

17. Post-injection Numeric Rating Scale (NRS) pain score

18. Adverse events, if they occurred

Questionnaires will be administered and collected from the participant through the University of Utah approved survey system of REDCap.

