### Objectives:

To assess changes in pain, physical function, and health-related quality of life in patients with post-amputation neuroma-associated residual limb pain after cooled radiofrequency ablation.

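### Pain is rated on one occasion before C-RFA, so drift before treatment cannot be seen; a second rating on the procedure day, before local anesthetic, is a cheap improvement

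*Combined protocol and SAP*

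**What the plan says.** The Procedures section sets one collection before treatment: "Baseline data will be collected within 2 weeks prior to the scheduled procedure". Each measure is listed once before the procedure. No run-in, diary, repeat rating or averaging is described.

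The baseline questions may be answered at the clinic appointment. If the patient "does not have time to do the baseline questions at time of appointment a qualified research staff member will call the patient to complete" them, this is done by phone. At that stage "the patient is being scheduled for residual limb neuroma radiofrequency ablation (RFA) procedure as standard of care", and consent is sought "once a standard of care treatment plan has been agreed upon by the patient and treating physician".

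Pain is recorded with the BPI, including the "numerical rating scale (NRS) score (worst, least, average, current"). The plan does not say which of the four items feeds the change score or the 50% rule. For the procedure day, the list gives only "Post-injection Numeric Rating Scale (NRS) pain score" and adverse events, both obtained after ablation.

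The objective is "To assess changes in pain, physical function, and health-related quality of life". The Data Analysis Plan uses more than 50% relief as the pain responder rule, and the Statistical analysis section gives means, SDs and proportions with 95% confidence intervals. No adjustment for baseline is planned. The Introduction calls the study a single-arm pilot meant to inform a randomized trial, yet also says it will define the attributable effect of cooled RFA.

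**The concern.** With no control arm, every baseline-referenced pain result is follow-up compared with one pre-treatment occasion. If that occasion falls when pain is above its usual level, later return to the usual level looks the same as benefit. A rating made when a procedure is being arranged is a plausible place for this to happen.

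The post-ablation score cannot serve as a second baseline, because local anesthetic is injected before the lesion and bupivacaine after it. The study therefore holds no data that could show whether pain was already falling before treatment, and a rating not collected then cannot be recovered later.

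Two smaller matters follow. A single rating carries its full day-to-day noise into the SD of change, a quantity the future trial may borrow. And the 2-week window runs from the scheduled date, so if a procedure is postponed, a baseline older than two weeks can still comply on a literal reading.

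**Working it through.** The plan gives no SD, effect size or variability for any pain measure, so there is no figure of its own to reproduce. The pain model below is assumed; only the sample sizes and the responder rule come from the documents.

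**Model 1 (flare).** 400,000 simulated patients with no treatment effect. Usual NRS has mean 5.5 and between-patient SD 1.2. Day-to-day SD s is 1.0 or 1.5. Ratings are whole numbers from 0 to 10. The first rating is raised by d (0, 0.5, 1.0 or 1.5), the procedure-day rating by d/2, and follow-up by 0.

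**Step 1: SD of change.**
- Single baseline: variance s² + s² = 2s².
- Mean of two ratings: s²/2 + s² = 1.5s².
- Ratio of SDs: √(1.5/2) = 0.866, a fall of about 13% whatever the value of d.
- Rounding adds 1/12 to each rating's variance. For s = 1.0: √(2 × 1.083) = 1.47 and √(1.5 × 1.083) = 1.27. For s = 1.5 the formula gives 2.16 and 1.87; simulation with the 0 and 10 limits gives 2.14 and 1.86.

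The 13% is a ceiling. It assumes independent ratings and no variation in true change. If true change varies with SD τ, the ratio is √[(1.5s² + τ²)/(2s² + τ²)]. Taking τ = s as an illustration gives √(2.5/3) = 0.913, a fall of about 9%.

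**Step 2: false mean fall.**
- Single baseline: d.
- Mean of two: (d + d/2)/2 = 0.75d.
- For d = 0.5 to 1.5 this is 0.5 to 1.5 points with one rating and 0.37 to 1.12 with two. For d = 0 both are about zero.

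The fall is the assumed flare handed back, and the reduction by a quarter follows from assuming it has half subsided by the procedure day. These figures set a scale; they are not evidence that a flare occurs.

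**Step 3: share passing a threshold with no treatment effect (range over s).**

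| | Single, >30% | Single, >50% |
|---|---|---|
| d = 0 | 10–19% | 1–5% |
| d = 0.5 to 1.5 | 15–35% | 2–10% |

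Much of the second row is ordinary noise already present in the first. With the mean of two ratings, the >30% share for d = 0.5 to 1.5 is 12–30%. The >50% share, which is the plan's pain rule, moves from 1.7% to 1.6% in the mildest flare case and from 10.1% to 8.8% in the most severe. With 20 patients, the latter is 0.013 × 20 = 0.26 of a patient.

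**Model 2 (selection).** Suppose patients are booked only when that visit's rating is at or above a cut c. Assume total SD 2.0, mean 5.5, single-rating ICC 0.5 to 0.8 and c from 4 to 7. The expected false fall is (1 − ICC) × SD × φ(t)/(1 − Φ(t)), with t = (c − 0.5 − 5.5)/2.
- ICC 0.5, c = 7: t = 0.5, so 0.5 × 2 × 0.352/0.309 = 1.14 (simulated 1.19).
- ICC 0.8, c = 4: t = −1, so 0.2 × 2 × 0.242/0.841 = 0.12 (simulated 0.13).
- No selection: 0.01 to 0.02.

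The share passing >50% stays under 5% throughout. At ICC 0.5 it is 4.2–4.8% with selection and 4.3% without.

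**Step 4: what the drift check can show.** With no drift, the difference between the two pre-treatment ratings has SD 1.47 to 2.14. The sample size reads 20 at Utah but 10 for all centers. The 95% half-width for mean drift is 2.09 × 1.47/√20 = 0.69 to 2.09 × 2.14/√20 = 1.00 for 20 patients, and 2.26 × 1.47/√10 = 1.05 to 2.26 × 2.14/√10 = 1.53 for 10. It can reveal a large drift but not settle a small one.

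**The case against.** A reader might infer that return from a flare is being counted as benefit, in every change score and responder rate. The documents do not support that.

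- Nothing says patients book during a flare. The readable eligibility criteria contain no minimum pain score (the third inclusion criterion cannot be read in the available text, so this stays open). They require pain beyond 6 months despite conservative therapy and a positive diagnostic block, which describes a chronic, multi-step pathway. This makes a high-day baseline less likely without excluding it.
- The appointment is not the only setting. A later phone call is allowed, and a baseline at the booking visit meets the window only if the procedure is scheduled within two weeks.
- The BPI includes an average-pain item, which should fluctuate less than current pain. This helps only if that item is used, and the plan does not say so.
- PGIC has no baseline, and the calculations above concern pain ratings only.
- The repair is partial. In Model 1 it leaves three quarters of the assumed bias, and a procedure-day rating may carry anticipation effects of its own.
- An SD from a single baseline is the right input for a future trial that also uses one.
- The scheduled date can be read as the date finally scheduled.

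All of this stands, and it limits the point to what the plan cannot see and what a second rating would add. It does not remove the point: the design has one pre-treatment occasion, no control and no means of detecting drift.

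**Conclusion.** The point holds as a cheap improvement, not as a demonstrated bias. Any elevation of baseline above usual pain would be counted as improvement and would go unseen. Its size is unknown: about zero if baselines are not elevated, and 0.13 to 1.5 points of mean NRS change across the flare and selection scenarios assumed here. Mean change is the exposed result; the >50% relief rate barely responds to the repair.

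The gain that needs no flare is precision: up to about 13% off the SD of change, given independent ratings and day-to-day SDs of 1.0 to 1.5, and less if true response varies between patients. The second gain is a direct, if imprecise, look at drift before treatment.

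Neither gain turns change after C-RFA into the attributable effect named in the Introduction. Placebo response, natural course and co-treatment remain, and only a control group addresses them.

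**What to change.** 1. Repeat the BPI/NRS pain items in REDCap on the procedure day, before any local anesthetic.
2. Define baseline pain as the mean of that rating and the existing pre-procedure rating, using the same named NRS item at both.
3. Report the mean and SD of the change between the two pre-treatment ratings as a descriptive check on drift. As a sensitivity analysis, report change to follow-up from each rating separately.
4. Count the 2-week window back from the procedure actually performed. A baseline that postponement pushes outside the window would then need to be repeated.

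The cost is a few survey items at a visit that already takes place, or a minute or two of participant time, with no extra visit. The reported improvement may come out slightly smaller. For comparison with a trial that uses one baseline, the single-rating SD of change remains available from item 3.

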**SOC Cooled Radiofrequency ablation (C-RFA) of Residual Limb Neuroma Procedure:**

*C-RFA:*

Our RFA procedures will be performed similar to methods described by Zhang et. al and Kim et. al with modification accounting for appropriate C-RFA technique. This technique is currently standard clinical practice at University of Utah outpatient clinic sites. During the C-RFA procedure, the participant will be positioned prone. The participant's skin will be prepared with chloroprep. An ultrasound probe will be placed on the participants' residual limb at a transverse angle in order to view the nerve and associated neuroma in long-axis. The probe will be advanced to the site of the stump neuroma. An 18-gauge C-RFA electrode with a 4mm active tip (Coolief® Cooled Radiofrequency Kit, Avanos Health Inc, Alpharetta, GA) will be placed adjacent to the neuroma. This needle will be connected via wire to a cooled radiofrequency generator. Motor testing will be performed (2.0 V, 2Hz). Sensory testing will be performed (1.0 V, 50Hz) to reproduce or exacerbate the RLP and / or PLP. At the site of the neuroma, 2 mL of local anesthetic will be injected through the needle (without triamcinolone as used per Zhang study). When the local anesthetic demonstrates pain relief, the needle will be placed into the nerve. C-RFA lesions will be created by using the typical C-RFA protocol with lesions performed for 165 seconds, with the RFA generator temperature set to 60°C (intralesional temperature >80 degrees). Once the procedure is completed, the needle will be removed. Following ablation, 0.5 mL of 0.5% bupivacaine will be injected at the site of the ablated neuroma to provide post procedure analgesia. No corticosteroids will be injected.

Following the Standard Treatment Procedure visit, routine scheduled follow-up will occur at 1 month (+/- 1 week), 3 months (+/- 2 weeks), 6 months (+/- 2 weeks), and 12 months (+/- 2 weeks) at which times all follow-up measures will be obtained. These questions will be administered over the phone or be sent to you using a secure REDCap survey by email. If received by email it will be in the form of two e-mail links in which you will again be asked questions regarding your pain level, changes in activity limitations, symptoms, emotions and

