overall quality of life related to your painful condition and to record current use of opioid and non-opioid analgesic use. This part of the survey should take 10 minutes.

This study is intended to monitor outcomes for 12 months following C-RFA of residual limb neuroma.

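### Adverse events are named for collection only on the day of ablation, so the 12 months of follow-up have no described adverse-event question

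*Combined protocol and SAP*

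**What the plan says.** In the Procedures section, the numbered list of data items ends with two that share one timing, introduced by "Immediately after ablation the following will be obtained": a pain score (item 17) and "Adverse events, if they occurred" (item 18). Just above them, a separate group of additions to the post-procedure survey holds only PGIC and a satisfaction score.

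The C-RFA procedure section says that "2 mL of local anesthetic will be injected through the needle" before lesioning and that "0.5 mL of 0.5% bupivacaine will be injected at the site of the ablated neuroma" afterwards. It then sets contacts at 1, 3, 6 and "12 months (+/- 2 weeks) at which times all follow-up measures will be obtained". These run by phone or emailed REDCap survey. The content is described to the participant as "you will again be asked questions regarding your pain level, changes in activity limitations, symptoms, emotions and" (continuing) "overall quality of life related to your painful condition and to record current use of opioid and non-opioid analgesic use". The same section gives 12 months as the period of outcome monitoring.

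Nothing else in the text supplied mentions collecting, grading or analysing adverse events. The Objectives name pain, physical function and health-related quality of life. The Data Analysis Plan and Statistical analysis sections name no safety outcome, although the latter provides proportions with 95% confidence intervals for categorical data in general.

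**The concern.** The one time at which adverse events are named is a poor time to be the only one. Local anesthetic has just been placed at the site, so local sensory symptoms may be masked. Infection, new weakness or altered sensation may also appear only days or weeks later.

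The later contacts are remote and their described questions concern the painful condition. A delayed harm that is not pain may show up in the symptom or activity items, but not systematically, and not with an onset date or the care sought. An adverse-event proportion built from item 18 would cover the procedure day only, yet a reader could take it as the safety result of a 12-month study.

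The Introduction gives the purpose of the pilot as informing a later randomized trial, and states that effectiveness outcomes for this technology are unpublished. Harms information is one of the things such a trial would want from the pilot.

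**Working it through.** The plan gives no adverse-event figure to reproduce, so the check is a comparison of the text with short arithmetic on the schedule.

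**1. Where adverse events are placed.**

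| Collection point | Content described | Adverse events named? |
|---|---|---|
| Immediately after ablation (items 17 and 18) | Pain score, adverse events | Yes |
| 1, 3, 6 and 12 months (C-RFA procedure section; PGIC and satisfaction from the Procedures list) | Pain, activity, symptoms, emotions, quality of life, analgesic use, PGIC, satisfaction | No, at any of the four |

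Collection points after the procedure: 1 + 4 = 5. Adverse events are named at 1 of 5.

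**2. Timing of the later contacts.** Taking 1 month as 30 days and 12 months as 365 days:
- first contact: 30 ± 7, that is day 23 to day 37;
- last contact: 365 ± 14, that is day 351 to day 379.

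The described adverse-event collection ends on day 0. The next contact of any kind is at least three weeks later.

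**3. What the sample can say about harms (context).** The Sample Size section gives 20 at Utah and 10 for all centers. These figures conflict, so both are used. With zero events among n participants, the upper limit of the exact two-sided 95% interval is 1 − 0.025^(1/n):
- n = 10: 1 − 0.025^(1/10) = 30.8%;
- n = 20: 1 − 0.025^(1/20) = 16.8%.

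The chance of seeing at least one event is 1 − (1 − p)^n. The rates p are assumed for illustration; the documents give none.

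| Assumed true rate p | n = 10 | n = 20 |
|---|---|---|
| 2% | 18% | 33% |
| 5% | 40% | 64% |
| 10% | 65% | 88% |

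Precision is low either way. These figures apply to delayed events only if participants are asked about them after day 0.

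**4. What cannot be computed.** The number of delayed events that would be missed cannot be estimated from the documents, because the existing symptom, activity and PGIC items may catch some.

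**The case against.** The strongest reply is that the follow-up description is not a full list. It is written to the participant, omits PGIC and satisfaction although the Procedures list assigns both to the post-procedure survey, refers to follow-up measures without itemizing them, and gives a duration for only one part of the survey. Silence on adverse events there is weak evidence, and the follow-up form was not available; the attachment mentioned is the baseline survey. This stands as a limit: the form may already contain the question. It does not remove the point. PGIC and satisfaction are missing from the description but are explicitly assigned to the survey, whereas adverse events are explicitly assigned to the immediate time point.

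Second, there is no safety objective, no safety outcome is analysed, and the protocol calls the procedure standard of care, with the questionnaires as the only research procedure. This is correct, and it is why no efficacy conclusion is in doubt. But the protocol chose to collect adverse events, so the period they cover should be explicit and should suit the stated follow-up.

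Third, 10 or 20 participants cannot characterize harms well. The upper limits of 30.8% and 16.8% confirm this. They are a reason for modest claims, not for leaving delayed events unasked.

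**Conclusion.** The concern holds, and the plan should be changed or clarified. As written, adverse events are collected at 1 of 5 post-procedure points, and collection stops on day 0 of about a year of follow-up. The pain, function and quality-of-life results are not affected. What is limited is the safety information available to the later trial.

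The conclusion rests on reading the lead-in to items 17 and 18 as fixing their timing, and on the follow-up form having no adverse-event item. The first is plain from the text. The second cannot be confirmed, so confidence is moderate and the remedy is conditional.

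**What to change.** **Collection.** Unless the follow-up survey already has one, add one adverse-event question at the 1, 3, 6 and 12 month contacts: any new or worse health problem since the last contact, its onset date and any care sought. Existing study staff classify seriousness from the answers. If item 18 was meant to repeat at these contacts, one sentence saying so is enough.

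**Reporting.** Report immediate events and cumulative 12-month events separately, as proportions of participants with exact (Clopper-Pearson) 95% confidence intervals. Give the number who answered the question at each contact, so that a missed contact is not read as no event.

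**Cost.** No new visits are needed. Assuming 1 to 2 extra minutes per contact, the addition is 4 × 1 = 4 to 4 × 2 = 8 minutes per participant over the year. The stated length for the described part of the survey is 4 × 10 = 40 minutes in total, so this is 10% to 20% more. Staff would review at most 4 × 10 = 40 or 4 × 20 = 80 responses, depending on which sample size applies.

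**Downsides.** Surveys become slightly longer, and some reported events will be unrelated to the procedure and need sorting. Onset dates rely on recall over gaps of up to a nominal six months. The plan should also confirm that the existing staff can take on the classification, since the documents do not describe this.
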